6.2.2. Treatment Compliance and Modifications

Subjects are expected to take all doses of study drug as instructed. At each visit, the number of syringes taken will be based on the drug accountability form and calculated by subtracting the number of syringes returned on the visit from the number of syringes dispensed in the previous visit.

The overall study drug compliance (%) will be calculated by dividing the total number of syringes taken across all visits by the total number of syringes intended across all visits and then multiplying by 100.

Compliance (%) = [(total no. of syringes dispensed – total no. of syringes returned) / (The actual duration of treatment (Days) *No. of syringes prescribed per day)] * 100

The actual duration of treatment (Days) will be calculated as

The actual duration of treatment (Days) = the last treatment date – the first treatment date

The overall study drug compliance will be summarized by treatment group.

A subject is considered compliant if overall study drug compliance is greater than or equal to 80% and less than or equal to 120%. A categorical summary of whether subjects were compliant (yes/no) will be presented.

Summary statistics on percentage of treatment compliance as well as the number and percentage of subjects in each compliance category (<80%, 80-120%, and >120% compliant) will be presented overall. Percentages will be calculated out of the number of subjects in the Full analysis Set.

7. Efficacy Analysis

All efficacy endpoints will be analyzed using FAS.

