8.6 TREATMENT EXPOSURE

Measures of extent of treatment exposure include the total number of doses per subject and compliance. Treatment compliance is defined as the number of doses administered per protocol/number of doses prescribed per protocol. These measures will be summarized using the Safety Set.

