6.2.1. Extent of Exposure

Duration of exposure is defined as the total number of days a subject is exposed to any study drug and will be presented as the total number of days from the first dose date (Day 1) to the last dose date (date of last dose minus the date of first dose + 1) as recorded on the End of Study/Early Withdrawal page on the CRF. If the last dose date on the End of Study/Early Withdrawal page is missing, or if a subject is lost to follow-up, but the drug accountability log confirms that the subject has taken study drug, the visit date following the last completed drug accountability log will be used.

The duration of exposure to study drug by treatment will be summarized for all subjects in the Safety Set and will be presented in a table by summary statistics. The duration of exposure will then be classified into one of the following categories: <= 7 days, 8 to 14 days, 14 to 28 days, 28 to 56 days, 56 to 84 days, and >= 84 days and will be presented as the number and percentage of subjects in each duration category. Percentages will be computed from the number of subjects in the Safety Set.

A summary of each subject's exposure will be presented in a listing.

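### SAP 6.2.2 leaves out the +1 day when it computes compliance, and the SAP 6.2.1 exposure classes overlap at 14, 28, 56 and 84 days; both faults are confined to descriptive tables

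*SAP*

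**What the plan says.** **Compliance.** SAP 6.2.2 describes compliance in words as "dividing the total number of syringes taken across all visits by the total number of syringes intended across all visits". The formula that follows puts syringes dispensed minus syringes returned over treatment duration times syringes prescribed per day. Duration is then defined: "The actual duration of treatment (Days) = the last treatment date – the first treatment date". Subjects from 80% to 120% inclusive count as compliant, and the table shows three classes (below 80%, 80-120%, above 120%). Protocol 8.6 words the measure differently: "Treatment compliance is defined as the number of doses administered per protocol/number of doses prescribed per protocol".

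**Exposure.** SAP 6.2.1 defines duration of exposure as "date of last dose minus the date of first dose + 1". The class limits listed there are "<= 7 days, 8 to 14 days, 14 to 28 days, 28 to 56 days, 56 to 84 days, and >= 84 days". Each subject is meant to have a single class, since durations are to be "classified into one of the following categories".

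**Context.** Injections are daily for 12 weeks (SAP 2.1). Day 1 and Week 12 are both dosed in clinic (Protocol section 4). SAP section 3 counts study days as the date difference plus 1, and sets the Week 12 target at day 84 with a window of 81 to 87. Neither document gives a tie rule for the exposure classes or corrects the duration formula elsewhere.

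**The concern.** Adjacent SAP sections count the same interval in two ways. When both the first and the last date carry a dose, the number of daily doses intended is the date difference plus 1. The 6.2.2 formula therefore contradicts its own verbal definition (taken over intended), the exposure definition in 6.2.1 and the SAP's study-day convention. Taken literally, it scores perfect dosing above 100%, scores one missed dose as exactly 100%, and fails for a subject with a single dose.

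In the exposure table, four values belong to two classes each. They are the target days for Weeks 2, 4, 8 and 12. The first boundary (7, then 8) is properly disjoint, so the overlap looks like a slip and not a convention. The value that matters most is 84, because it decides whether a completer dosed on the target day is shown in the top class. What is at stake is a correct compliance summary and a reproducible exposure table.

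**Working it through.** The plan gives no worked compliance or exposure figure to reproduce, so the check applies the SAP's own rules.

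**Inputs.** One syringe per day (SAP 2.1). D = number of dosing days counted inclusively, that is last date - first date + 1 (SAP 6.2.1). The SAP 6.2.2 duration is then D - 1. Limits are 80% and 120%, both inclusive (SAP 6.2.2).

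**Step 1: full adherence.** Syringes taken = D, so SAP 6.2.2 gives 100 × D/(D - 1). With the +1 restored it gives 100 × D/D = 100% at every D.

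| D | SAP 6.2.2 | Class |
|---|---|---|
| 1 | 1/0, undefined | none |
| 2 | 2/1 = 200% | >120% |
| 5 | 5/4 = 125% | >120% |
| 6 | 6/5 = 120.0% | 80-120% |
| 7 | 7/6 = 116.7% | 80-120% |
| 14 | 14/13 = 107.7% | 80-120% |
| 28 | 28/27 = 103.7% | 80-120% |
| 56 | 56/55 = 101.8% | 80-120% |
| 84 | 84/83 = 101.2% | 80-120% |

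A fully adherent subject is classed above 120% when D > 1.2 × (D - 1), that is when D < 6. Across the Week 12 window (D = 81 to 87) the value runs from 101.25% to 101.16%. One missed dose in 84 gives 83/83 = 100%.

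**Step 2: subjects near a cut-off.** With k syringes taken:

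- The lower class is wrong when 0.8(D - 1) ≤ k < 0.8D, an interval 0.8 of a syringe wide.
- The upper class is wrong when 1.2(D - 1) < k ≤ 1.2D, an interval 1.2 syringes wide.

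At D = 84:

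- k = 67: 67/84 = 79.76% becomes 67/83 = 80.72%, so a subject below 80% is called compliant. The effective threshold is 67 syringes where it should be 68 (68/84 = 80.95%).
- k = 100: 100/84 = 119.05% becomes 100/83 = 120.48%, so a compliant subject moves above 120%.

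At D = 14 the same happens at k = 11 (78.57% becomes 84.62%) and k = 16 (114.29% becomes 123.08%).

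**Step 3: exposure classes.** Every whole day from 1 to 99 was tested against the six classes. Each day has at least one class, and exactly four have two:

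- 14: 8 to 14, and 14 to 28
- 28: 14 to 28, and 28 to 56
- 56: 28 to 56, and 56 to 84
- 84: 56 to 84, and 84 or more

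A subject whose last dose is on study day 84 has exposure of exactly 84 days. SAP 6.2.1 also substitutes a visit date when the last-dose date is missing, so an on-target visit at Week 2, 4, 8 or 12 lands on a shared value too.

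**The case against.** The strongest reply is that little turns on this, and several larger inferences are indeed not supported.

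- **A reader might infer that the compliance table is wrong for ordinary subjects.** A fully adherent completer reads about 1.2 points too high and stays in the 80-120% class. The class moves only in the cases in Steps 1 and 2, and the documents do not say how many such subjects there will be.
- **A reader might infer that the exposure percentages will sum to more than 100%.** SAP 6.2.1 assigns each subject to one class, so double counting is not prescribed. The defect is a missing tie rule.
- **A reader might infer that 84 days will be the most common exposure.** It is the target, but the window is 81 to 87, and a visit booked exactly 12 calendar weeks after Day 1 is day 85. The number at exactly 84 cannot be known from the documents.
- **A reader might infer that the SAP misclassifies early stoppers by departing from Protocol 8.6.** A subject who takes every dose and stops at day 28 reads 103.7% under the SAP, against 28/84 = 33.3% if the protocol means the full course. But Protocol 8.6 does not say whether doses after stopping count as prescribed, and compliance while on treatment is a legitimate measure. Early stopping is reported separately, through exposure (SAP 6.2.1) and discontinuation reasons (SAP 4.1).
- **A reader might infer that efficacy results are affected.** No efficacy model uses the compliance flag, and no analysis-set definition refers to it. The Per Protocol Set in Protocol 8.4.4 rests on post-dose ALP data and the Medical Monitor's judgement. The SAP introduction also describes this document as covering the interim analysis, so an effect on the final report is not shown.

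These replies limit the reach of the point. None of them repairs the missing +1 or supplies a tie rule.

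**Conclusion.** The point holds as two drafting errors of minor weight. The 6.2.2 duration is one day short of the number of dosing days, so it overstates compliance by a factor of D/(D - 1). The excess is negligible for most completers, material for very short exposures, and leaves no value for a single dose. The exposure classes give no unique answer at four values, of which 84 matters most.

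The compliance result assumes one syringe per day and a dose on both the first and the last treatment date, as the documents state. The exposure result needs no assumption beyond the listed class limits. The effect is confined to descriptive tables under this SAP.

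**What to change.** 1. In SAP 6.2.2, set treatment duration to last treatment date - first treatment date + 1, matching 6.2.1.
2. In SAP 6.2.1, make the classes mutually exclusive and state where day 84 belongs. One option is ≤7, 8-14, 15-28, 29-56, 57-83 and ≥84 days; another ends with 57-84 and >84. Both remove the overlap. The first puts completers with 81 to 83 days, who are within the visit window, in the lower class. The second also puts the subject dosed last on day 84 there. The sponsor should choose and record the choice before the tables are run.

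The cost is two lines of SAP text and the matching programming, with no change to data collection, design or the primary analysis.

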7.1. Primary Efficacy Endpoint

The primary efficacy endpoint is the mean change in ALP from Baseline at Week 12.

7.1.1. Primary Analysis

The primary analysis will be performed on the FAS to evaluate the treatment effect of NGM282. The mean change in ALP from Baseline at Week 12 will be compared between each of the two treatment groups (NGM282 1 mg or 3 mg, as applicable) and the placebo group.

Mixed-effect model repeated measures (MMRM) analysis of covariance (ANCOVA) of mean change in ALP from Baseline at Week 12 will be used to compare the difference between treatment groups. Mathematically stated:

H_0 : Mean change in ALP from Baseline at Week 12_{NGM282 1 mg} = Mean change in ALP from Baseline at Week 12_{placebo},

and

Mean change in ALP from Baseline at Week 12_{NGM282 3 mg} = Mean change in ALP from Baseline at Week 12_{placebo}

H_1 : Mean change in ALP from Baseline at Week 12_{NGM282 1 mg} \neq Mean change in ALP from Baseline at Week 12_{placebo},

[figure not shown]
or

Mean change in ALP from Baseline at Week 12_{NGM282 3 mg} \neq Mean change in ALP from Baseline at Week 12_{placebo}

Mean change in ALP from Baseline at Week 12 will be evaluated using the MMRM analysis adjusting for treatment group, visit, treatment group by visit interaction, UDCA use, treatment group by UDCA use interaction as classification variables and the Baseline value as covariate. For each treatment and treatment comparison versus placebo, the least squares mean, associate standard error (SE), 95% confidence interval and corresponding p-value will be present. The overall type I error rate for the two primary comparisons versus placebo will be controlled using the step-down Dunnett multiple-testing procedure [Dmitrienko and D'Agostino (2013)].

With the same model, linear combinations $\mu_1 - \mu_3$ and $(\mu_1 + \mu_3)/2 - \mu_p$ will be estimated, where μ_1 , μ_3 , and μ_p are the population LS means for the primary efficacy endpoint of the 1 mg NGM282, 3 mg NGM282, and placebo groups, respectively.

The relevance of the explanatory variables to the mean change in ALP from Baseline at Week 12 will be checked. All relevant explanatory variables will be included in the primary analysis model with FAS.

7.2. Secondary Efficacy Endpoint

The following endpoints will be analyzed for the FAS.

[figure not shown]
The endpoints among the following that are based on assessments scheduled for more than 1 post-treatment time point, will be analyzed using the FAS. They will be evaluated using MMRM analyses similar to that of the primary endpoint analysis. In contrast, the endpoints among the following based on assessments scheduled at Week 12 only will be evaluated using an ANCOVA model including treatment group, UDCA use, and treatment by UDCA use interaction as classification variables, and the Baseline value as the continuous covariate.

- Percent change from Baseline in ALP at Week 12
- Changes and percent changes from Baseline at Week 12 in the following:
 - ALT, AST, bilirubin (total, direct), and GGT
 - Total cholesterol, HDL cholesterol, LDL cholesterol, and triglycerides
 - Bile-mediated absorption as measured by fat-soluble vitamins

For each NGM282 treatment group, the LS mean rate (slope, per week) of change in ALP during weeks 1-4 will be compared to that during weeks 5-12. Changes in the slopes will be estimated with a MMRM from primary analysis. The same analysis will be done for percent change in ALP.

The relevance of the explanatory variables to each secondary efficacy endpoint will be checked. Similar to the model in the primary efficacy analysis, all relevant explanatory variables will be included into the analysis model with FAS.

The Mayo Partial IBD Score is a non-invasive 9-point partial Mayo score used as an outcome measure for clinical trials assessing therapy for ulcerative colitis. The Mayo Partial IBD Score will be assessed at all study visits. It is administered pre-dose at Day 1 and Weeks 1, 2, 4, 8, 12 and 16 (End of study). Severity of IBD-associate symptoms will be summarized with frequency and percentage.

8. Safety and Tolerability Analysis

Safety and tolerability will be assessed by clinical review and summaries of the following parameters:

1. AEs
2. Clinical laboratory test results
3. Physical examination results
4. LISSAs
5. Electrocardiogram results

6. Pregnancy Test
7. Vital signs

[figure not shown]
All safety and tolerability analyses will be conducted using the Safety Set. Percentage for the safety and tolerability analyses based on the number of subjects with a given event or attribute will be based on the number of subjects who were treated.

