C4 = 7-alpha-hydroxy-4-cholesten-3-one; CA19-9 = carbohydrate antigen 19-9; ELF = enhanced liver fibrosis; EOS = End of Study; EOT = End of Treatment; ERCP = endoscopic retrograde cholangiopancreatography; HIV = human immunodeficiency virus; IBD = inflammatory bowel disease; INR = International Normalized Ratio; LISSA = local injection-site symptom assessment; MRCP = magnetic resonance cholangiopancreatography; NRS = Numeric Rating Scale; p-ANCA = perinuclear anti-neutrophil cytoplasmic antibodies; PK = pharmacokinetic; Wk = week.

^a There must be a minimum of 14 days between Screening and Day 1 visits for adequate separation of the repeated Chemistry (liver function tests) and INR assessments.

^b Colonoscopy will be performed only in patients with concomitant IBD and who do not have a colonoscopy available within 12 months of Screening.

^c MRCP will be performed in all subjects at Screening.

^d LISSA evaluations will be performed pre-dose for all on-treatment visits.

^e PK blood samples will be collected before subjects dose themselves in the clinic (pre-dose). At Day 1 and Week 12, an additional PK blood sample will be collected 2 hours post-dose.

^f NRS Itch/Fatigue will be completed as a daily diary during Day 1 and Study Weeks 1, 4, and 12. Diary will be dispensed at the study visit prior to the collection week.

^g Mayo Partial IBD Score will be collected in all patients, independent of whether they have IBD or not.

^h A second CA19-9 sample may be collected during the Screening period a minimum of 4 weeks from the original Screening sample in order to meet Inclusion Criteria 3g.

ⁱ A serum pregnancy test will be performed on all female subjects at Screening, Week 12, and Week 16. A urine pregnancy test will be performed on all female subjects at Day 1 (pre-dose).

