8.9.3 Analysis of Secondary Endpoints

The analysis of secondary endpoints will be based on the FAS.

The primary efficacy analysis will be repeated for each continuous secondary efficacy endpoint. Further explanatory variables may be included in the modeling depending on the relevance to the endpoint analyzed and will be specified in the SAP.

In addition, for each NGM282 treatment group, the LS mean rate (slope, per week) of change in ALP during Weeks 1–4 will be compared to that during Weeks 5–12; the changes in slopes will be estimated. This estimation will be performed using a MMRM similar to that of the primary efficacy analysis. It will also be repeated using percent change in ALP.

Categorical secondary efficacy endpoints (reflecting incidence and severity of IBD-associated symptoms and acute cholangitis) will be analyzed using confidence intervals of differences of population treatment proportions.

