APPENDIX D—MAYO PARTIAL IBD SCORE (INFLAMMATORY BOWEL DISEASE SCALE)

Components of the Partial Mayo Score

Stool Frequency

0 = Normal

1 = 1–2 stools/day more than normal

2 = 3–4 stools/day more than normal

3 = >4 stools/day more than normal

Rectal bleeding^a

0 = None

1 = Visible blood with stool less than half the time

2 = Visible blood with stool half of the time or more

3 = Passing blood alone

Physician rating of disease activity

0 = Normal

1 = Mild

2 = Moderate

3 = Severe

^a A score of 3 for bleeding required patients to have at least 50% of bowel motions accompanied by visible blood and at least one bowel motion with blood alone.

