2.2. Study Endpoints

The primary efficacy endpoint is defined as the mean change in ALP from Baseline at Week 12.

The secondary efficacy and PD endpoints are the following:

- Percent change from Baseline at Week 12 in ALP
- Changes and percent changes from Baseline at Week 12 in the following
 - ALT, AST, bilirubin (total, direct), and GGT
 - Total cholesterol, HDL-cholesterol, LDL-cholesterol, and triglycerides
 - Bile-mediated absorption as measured by fat-soluble vitamins
- Severity of IBD-associated intestinal symptoms

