2.3. Treatments

Subjects will be instructed to self-administer/dose at approximately the same time each morning in the whole treatment period. Blinded study drug (NGM282 or placebo) will be administered as a subcutaneous (SC) injection in the abdomen. Subjects will be trained on self-administering a

SC injection. Self-administration will occur in clinic under the observation of clinic staff on weeks 1, 2, 4, 8, and 12.

3. General Statistical Considerations

Continuous data will be summarized using descriptive statistics (i.e. n, mean, standard deviation, median, minimum, and maximum). Categorical data will be summarized using the subject count and percentage in each category. For the summary statistics of all numerical variables, unless otherwise specified, minimum and maximum will be displayed to the same level of precision as the reported data. Mean and median will be displayed to one level of precision greater than the data collected. Standard deviation/standard error will be displayed to two levels of precision greater than the data collected. P-values will be rounded to three decimal places. If a p-value is less than 0.001 it will be reported as “<0.001.” If a p-value is greater than 0.999 it will be reported as “>0.999.”

Data will be displayed in all listings sorted by treatment group. Subjects will be identified in the listings by the subject identification number concatenated with the investigator number.

When count data are presented, the percentage will be suppressed when the count is zero in order to draw attention to the non-zero counts. The denominator for all percentages will be the number of subjects in that treatment within the analysis set of interest, unless otherwise specified.

Unless otherwise specified, Baseline will be defined as the last non-missing evaluation prior to or on the date of study drug SC injection (Day 1).

The study day will be calculated as follows:

If the assessment date occurs on or after the date of NGM282 SC injection (Day 1):

Study day = assessment date – date of NGM282 SC injection (Day 1) + 1.

If the date of interest occurs before the date of NGM282 SC injection (Day 1):

Study day = assessment date – date of NGM282 SC injection (Day 1)

[figure not shown]
There is no study day 0.

For all efficacy analyses, analysis visit windows will be used for assigning assessments to an analysis visit, as follows:

Scheduled Visit	Target Day	Visit Window (Days)
Screening	-42 to -1	Not applicable

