C4 = 7-alpha-hydroxy-4-cholesten-3-one; CA19-9 = carbohydrate antigen 19-9; ELF = enhanced liver fibrosis; EOS = End of Study; EOT = End of Treatment; ERCP = endoscopic retrograde cholangiopancreatography; HIV = human immunodeficiency virus; hs-CRP = high-sensitivity C-reactive protein; IBD = inflammatory bowel disease; INR = International Normalized Ratio; LISSA = local injection-site symptom assessment; MRCP = magnetic resonance cholangiopancreatography; NRS = Numeric Rating Scale; p-ANCA = perinuclear anti-neutrophil cytoplasmic antibodies; PK = pharmacokinetic; TSH = thyroid-stimulating hormone; Wk = week.

^a There must be a minimum of 14 days between Screening and Day 1 visits for adequate separation of the repeated Chemistry (liver function tests) and INR assessments.

^b Colonoscopy will be performed only in subjects who do not have a colonoscopy available within 12 months of Screening.

^c MRCP will be performed in all subjects at Screening.

^d LISSA evaluations will be performed pre-dose for all on-treatment visits.

^e PK blood samples will be collected before subjects dose themselves in the clinic (pre-dose). At Day 1 and Week 12, an additional PK blood sample will be collected 2 hours post-dose.

^f NRS Itch/Fatigue will be completed as a daily diary during Study Weeks 1, 4, and 12. Diary will be dispensed at the study visit prior to the collection week.

^g Mayo Partial IBD Score will be collected in all subjects, independent of whether they have IBD or not.

^h A second CA19-9 sample may be collected during the Screening period a minimum of 4 weeks from the original Screening sample in order to meet Inclusion Criteria 3g.

ⁱ A serum pregnancy test will be performed on all female subjects at Screening, Week 12, and Week 16. A urine pregnancy test will be performed on all female subjects at Day 1 (pre-dose).

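### SAP 7.2 pools subjects with and without IBD when it summarizes IBD-symptom severity, so drug diarrhea can appear as IBD activity, and this SAP omits the protocol's interval against placebo without recording it

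*SAP*

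**What the plan says.** **Who is scored.** Footnote g to the schedule of procedures says the same in both documents. In the Protocol (5.5) it reads "Mayo Partial IBD Score will be collected in all patients, independent of whether they have IBD or not"; in the SAP (13.1), "Mayo Partial IBD Score will be collected in all subjects, independent of whether they have IBD or not".

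**Who is counted.** The opening line of SAP Section 7 is "All efficacy endpoints will be analyzed using FAS". SAP Section 3 sets the default that "The denominator for all percentages will be the number of subjects in that treatment within the analysis set of interest", unless something else is specified. SAP 7.2 specifies nothing else for this endpoint. SAP 5.2 limits baseline disease characteristics to UDCA use and duration of PSC, so IBD status is not among them.

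**What the score counts.** Protocol Appendix D gives three items of 0 to 3 points each: stool frequency, rectal bleeding and physician rating. The first step on the stool item is "1 = 1–2 stools/day more than normal", with no reference to cause. Neither document says how the 0 to 9 score becomes a severity category, or which visit is tabulated.

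**How the arms are compared.**

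| | Protocol | SAP |
|---|---|---|
| Objective | Compare incidence and severity (Section 3) | Same (1.2) |
| Endpoint | Incidence and severity (8.9.1) | "Severity of IBD-associated intestinal symptoms" (2.2) |
| Analysis | Categorical secondary endpoints "will be analyzed using confidence intervals of differences of population treatment proportions" (8.9.3) | "Severity of IBD-associate symptoms will be summarized with frequency and percentage" (7.2) |

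SAP Section 11 lists the analyses taken out: pruritus and fatigue, acute cholangitis, C4 and bile acids, microbiome and PK. The IBD endpoint is not on that list.

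**The concern.** The secondary question is whether NGM282 changes intestinal symptoms of IBD. Protocol 2.4 reports that diarrhea was the commonest treatment-related event in the 28-day primary biliary cirrhosis (PBC) trial, and more frequent on active drug than on placebo. A scale with one third of its points on stool count, tabulated over everyone, does not separate that drug effect from IBD activity. The error can run either way. Diarrhea in subjects without IBD can look like IBD worsening on NGM282, while subjects with neither IBD nor diarrhea add zeros that shrink a real change in those who have IBD.

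The interim analysis is unblinded and is meant to inform whether the study continues (Protocol 8.10.9). An IBD-symptom table that mixes the two effects, with no statement of uncertainty, is a poor input to that decision.

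**Working it through.** **1. Does the SAP pool?** It never uses the word. Pooling follows from three rules together: the score is taken in everyone, efficacy uses the FAS, and the denominator is the whole arm within the FAS unless stated otherwise. No exception is stated.

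**2. The plan's own diarrhea rates (Protocol 2.4).** 3/14 = 21.4% on 0.3 mg, 4/16 = 25.0% on 3.0 mg and 1/15 = 6.7% on placebo. All three reproduce. That trial had no 1 mg arm.

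**3. Cases from subjects without IBD.** Inputs: 20 randomized per arm (Protocol 8.1), at least 8 completers per arm at the interim (Protocol 8.10.9), and IBD prevalence in PSC of 21% to 80% (Protocol 2.1.1), taken as an assumed range for this trial. Also assumed: the PBC rates apply here, equally with and without IBD, and each case scores on the Mayo item.

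Expected cases = arm size × (1 − prevalence) × diarrhea rate.

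| | 80% have IBD | 21% have IBD |
|---|---|---|
| Without IBD, per 20 | 20 × 0.20 = 4.0 | 20 × 0.79 = 15.8 |
| Cases on 3 mg | 4.0 × 0.25 = 1.0 | 15.8 × 0.25 = 3.95 |
| Cases on placebo | 4.0 / 15 = 0.27 | 15.8 / 15 = 1.05 |
| Without IBD, per 8 | 8 × 0.20 = 1.6 | 8 × 0.79 = 6.3 |
| Cases on 3 mg | 0.4 | 1.6 |
| Cases on placebo | 0.1 | 0.4 |

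**4. Pooled difference when the drug has no effect on IBD.** Let *q* be the share with IBD, *f* the symptom rate from IBD itself in those subjects (same in both arms, assumed 10% to 30%), and *d* the diarrhea rate, independent of *f*.

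- Pooled rate = q[1 − (1 − f)(1 − d)] + (1 − q)d = d + qf(1 − d).
- Difference, 3 mg minus placebo = (0.250 − 0.067)(1 − qf) = 0.183 × (1 − qf).
- Smallest qf = 0.21 × 0.10 = 0.021: 0.183 × 0.979 = 0.179.
- Largest qf = 0.80 × 0.30 = 0.24: 0.183 × 0.76 = 0.139.

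The pooled table would show an excess of about 14 to 18 points on 3 mg with no change in IBD at all. Within the IBD subset alone (q = 1) the excess is 0.183 × (1 − f), or 0.128 to 0.165. Splitting by IBD status therefore does not by itself remove drug diarrhea; the three items must also be shown separately.

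**5. Dilution.** If the drug changed the symptom rate in IBD subjects by Δ and there were no diarrhea elsewhere, the pooled table would show qΔ, that is 0.21Δ to 0.80Δ.

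**6. What a restored interval would look like.** The Protocol names no interval type. As an illustration, the Newcombe 95% interval (built from Wilson limits), with the PBC rates and all subjects in the arm:

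- 20 per arm, 25.0% against 6.7%: difference 18.3 points, interval −5.3 to 40.8.
- 20 per arm in whole counts, 5/20 against 1/20: Wilson limits 0.112 to 0.469 and 0.009 to 0.236. Lower = 0.20 − √[(0.25 − 0.112)² + (0.236 − 0.05)²] = −0.032. Upper = 0.20 + √[(0.469 − 0.25)² + (0.05 − 0.009)²] = 0.423.
- 8 per arm, same rates: 18.3 points, interval −20.1 to 52.9.

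**The case against.** **Scope.** SAP Section 1 says the document describes the interim analysis, and SAP Section 10 mentions a Full Study SAP that was not supplied. A reader might infer that the comparison with placebo has gone from the trial and the IBD question can no longer be answered. The documents do not support that. The omission is shown for this SAP only, Protocol 8.9.3 still governs the final analysis, and percentages by arm allow an informal comparison meanwhile.

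**Meaning of no IBD.** A reader might infer that a raised score in a subject without IBD cannot be an IBD symptom. That goes too far. Protocol 5.2 (criterion 9) and footnote b in 5.5 limit screening colonoscopy to patients with concomitant IBD, so absence of IBD is a history label rather than a verified finding. Scoring everyone is a sensible way to notice new onset, and those subjects should not be dropped.

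**Transfer of rates.** A reader might infer that 5 against 1 subjects per arm (20 × 0.25 = 5; 20 / 15 = 1.3) would gain stool points. The rates are adverse events over 28 days in another disease, while the Mayo score is taken at visits. A short episode between visits may score nothing. The figures in steps 3, 4 and 6 show scale; they are not predictions.

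**Diarrhea is visible elsewhere.** Gastrointestinal events are tabulated by lowest level term and by relationship (SAP 8.1 to 8.1.2), and recorded IBD should appear in medical history (SAP 5.3). Two of the three Mayo items are not stool counts. This softens the point, but no planned table crosses symptom score with IBD status.

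**Incidence and precision.** A severity table with a none category would show incidence in effect, but no such category is defined. Small subsets will give wide intervals. That is a reason to show the uncertainty, though it limits what the interim can tell.

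**Conclusion.** The point holds for this SAP. Its rules pool subjects with and without IBD on a score that responds to stool count whatever the cause, for a drug with a known diarrhea signal. Under the stated assumptions (PBC adverse-event rates carrying over to visit scores, equal rates with and without IBD, 21% to 80% IBD prevalence), subjects without IBD would add about 1 to 4 cases per 20 on 3 mg and 0.3 to 1 on placebo. A 14 to 18 point pooled excess could then arise with no effect on IBD; that range also assumes a 10% to 30% background symptom rate in IBD subjects.

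Separately, and without any assumption, the SAP keeps the comparative objective but lists severity only, gives no interval and does not record the change. This is a secondary endpoint with no stated power, so the consequence is a misleading or uninformative table. The primary analysis is not affected.

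**What to change.** In SAP 7.2, and carried into the full-study SAP:

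- Present the endpoint by baseline IBD status, with the IBD subset as the main display. Keep subjects without known IBD in a separate display so that new-onset symptoms stay visible. Add IBD status to the baseline disease characteristics in SAP 5.2.
- Show stool frequency, rectal bleeding and physician rating separately, as change from Day 1. State the visit and the rules that define severity categories and worsening.
- Give the difference from placebo in the proportion worsening with a 95% confidence interval, as Protocol 8.9.3 requires. Otherwise record and justify in Section 11 that the interval, and incidence as an endpoint, are omitted from this SAP.

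The cost is a few more tables. The item scores are already collected, and IBD status has to be known to apply inclusion criterion 5. The drawback is small IBD denominators: about 4 to 16 per arm of 20 (20 × 0.21 = 4.2; 20 × 0.80 = 16), and about 2 to 6 per arm of 8 at the interim (8 × 0.21 = 1.7; 8 × 0.80 = 6.4). The intervals will generally be wider than those in step 6 and should be read as descriptive.
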